3. POPULATIONS FOR ANALYSES

The study data will be analyzed in one of the following analysis populations:

The **Per-Protocol (PP)** population will include all randomized subjects who follow the protocol without any major deviation(s) that could impact the integrity of the data. Reasons for exclusion from the PP population may include:

- use of the incorrect study spectacles
- poor compliance with the wearing regimen.

The **Safety** population will include all randomized subjects who use any of the study devices. Subjects will be grouped for analysis based on the actual device used.

4. STATISTICAL ANALYSES

4.1 GENERAL APPROACH

The analyses will be performed once all data have been entered into the EDC, cleaned and the database has been locked.

Descriptive summaries will include mean, standard deviation, median, and range for continuous variables and counts and percentages for categorical variables. Two-sided 95% confidence intervals (CIs) will be provided for the means and percentages. For key outcome measures, the difference between each of the test arms versus the control and the 95% CI of the difference will be computed.

All statistical analysis will be performed using SAS® (Version 9.4 or higher, SAS Institute Inc., Cary, NC, USA). Some graphical tools (such as EXCEL, PowerPoint) may be used to generate figures.

4.2 ANALYSIS OF THE STUDY CONDUCT

The number of subjects who are enrolled, discontinue (early discontinuation of treatment or early termination from the study), and complete the study (through 6 months after randomization) will be tabulated.

Reasons for early discontinuation of the treatment or early termination of from the study will be listed and summarized by treatment arm. Any eligibility criteria exceptions and other protocol deviations will also be summarized by treatment arm.

4.3 ANALYSIS OF TREATMENT COMPARABILITY

Demographic and baseline characteristics such as age, gender and race will be summarized for all randomized subjects. Other baseline characteristics such as baseline axial lengths will be summarized for all randomized subjects by treatment.

4.4 ANALYSIS OF THE PRIMARY EFFICACY ENDPOINTS

The main analysis of the primary efficacy outcome measures (i.e., change from baseline in axial length) will be on the PP population.

A mixed effect model including the following terms will be used to analyze the difference in change in axial length between treatments: treatment, order, age, gender, and treatment-by-order interaction as factors, and the baseline axial length as a covariate. Estimates for the mean change from baseline at 6 months will be calculated from the model [i.e., least-squared (LS) means]. The standard error and 95% confidence interval (CI) of the LS mean will be provided. The difference in LS mean change from baseline between the test and the control lens and the corresponding 95% CI will be derived from the model. If the upper limit of the CI is less than the non-inferiority bound of 0.03 mm, then the hypothesis of the test lens being non-inferior to the control lens will be met. Also, the p-values for testing the pairwise differences in LS means against a zero value will be computed based on t-tests.

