9.2 SAMPLE SIZE DETERMINATION

The study is sized to ensure an adequate power at an overall alpha level of 0.05 for treatment comparisons in axial length change from baseline at 6 months.

Assuming a drop-out rate of 10-20%, a study of 50-60 subjects achieves 80% power to detect non-inferiority

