2. SAMPLE SIZE DETERMINATION

The study is sized to ensure an adequate power at an overall alpha level of 0.05 for treatment comparisons in axial length change from baseline at 6 months. Assuming axial length change from baseline has a standard deviation (SD) of approximately 0.31 mm at 12 months²⁸. Therefore, it can be assumed that the SD at 6 months (SD_{6m}) is ≤ 0.31 mm. It has also been assumed that there will be no difference in mean AL change between the test and control lens types.

Power	80%
SD at 6m (each eye)	0.095
Between-eye correlation	0.85
SD of DDAL	0.053
True Difference in DDAL	0.00 mm
Equivalent/NI Margin	0.03 mm

Assuming a drop-out rate of 10-20%, a study of 50-60 subjects achieves 98% power to detect non-inferiority using a one-sided t-test when the margin of non-inferiority is 0.03 mm and the true difference between the treatments is 0.00 mm. The data are drawn from a single population with a standard deviation of 0.053 and the significance level (alpha) of the test is 0.050.

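### The SAP's 98% power is for a one-sided test at alpha 0.050, but its success rule uses a 95% CI, most naturally a one-sided 0.025 test with 93.7% to 98.3% power

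*SAP*

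**What the plan says.** SAP Section 2 (Sample Size Determination) says that "a study of 50-60 subjects achieves 98% power to detect non-inferiority using a one-sided t-test", and that "the significance level (alpha) of the test is 0.050". Its inputs are a between-eye difference SD of 0.053 mm, a margin of 0.03 mm, a true difference of zero and 10-20% drop-out.

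SAP 4.4 (Analysis of the Primary Efficacy Endpoints) sets the success rule. The difference in LS means between "the test and the control lens and the corresponding 95% CI will be derived from the model", and then: "If the upper limit of the CI is less than the non-inferiority bound of 0.03 mm", non-inferiority is declared. Section 4.4 does not state the sidedness of the interval.

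SAP 4.1 (General Approach) gives the only convention: "Two-sided 95% confidence intervals (CIs) will be provided for the means and percentages". For key outcomes it then adds that "the difference between each of the test arms versus the control and the 95% CI of the difference will be computed", without repeating the sidedness.

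Protocol 9.2 gives an overall alpha of 0.05, shows no sidedness, and says that "a study of 50-60 subjects achieves 80% power to detect non-inferiority".

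**The concern.** A power statement should describe the test that decides the trial. The upper limit of a two-sided 95% CI falls below the margin exactly when a one-sided test at 0.025 rejects. The sizing test is one-sided at 0.05, which corresponds to a two-sided 90% CI or a one-sided 95% upper bound. If the interval in SAP 4.4 is two-sided, as the wording most naturally suggests, the alpha and the 98% in Section 2 do not belong to the rule in Section 4.4.

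Two things are at stake. The plan misstates the operating characteristic of its primary test. And because the sidedness of the deciding interval is not written down, a borderline result could be judged under either reading after the data are seen.

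**Working it through.** **Inputs (SAP Section 2).** SD of the between-eye difference 0.053 mm; margin 0.03 mm; true difference 0; 50-60 enrolled; drop-out 10-20%. Each child wears both lenses (Protocol 6.3), so there is one paired difference per child.

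**Evaluable children.** 50 × 0.8 = 40; 50 × 0.9 = 45; 60 × 0.8 = 48; 60 × 0.9 = 54.

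**Formula.** One-sample t-test on the paired difference, the method of SAP Section 2:

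- df = n − 1
- noncentrality = 0.03 / (0.053/√n)
- power = P(noncentral t with these parameters > t critical value at 1 − α)

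**Reproducing the plan's figure.** At n = 45 the standard error is 0.053/√45 = 0.00790 and the noncentrality is 0.03/0.00790 = 3.80. At one-sided 0.05 the critical value is 1.680 and power is 98.2%. The stated 98% reproduces, and 45 is the smallest n that reaches it.

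**Power under the rule in SAP 4.4.** With one-sided 0.025 (critical value 2.015 at n = 45) and everything else unchanged:

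| Evaluable n | Noncentrality | Power, one-sided 0.05 (SAP Section 2) | Power, two-sided 95% CI rule | Loss (points) |
|---|---|---|---|---|
| 40 | 3.58 | 96.9% | 93.7% | 3.2 |
| 45 | 3.80 | 98.2% | 96.0% | 2.2 |
| 48 | 3.92 | 98.7% | 97.0% | 1.7 |
| 54 | 4.16 | 99.3% | 98.3% | 1.0 |

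Of the four scenarios, only 54 evaluable reaches 98% under the CI rule. A simulation of 200,000 trials per n agrees: 98.2% and 95.9% at n = 45, and 99.3% and 98.3% at n = 54.

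**Numbers needed.**

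| Target power | Evaluable, one-sided 0.05 | Evaluable, 95% CI rule |
|---|---|---|
| 98% | 45 | 53 |
| 80% | 21 | 27 |

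For 98% the enrolment is:

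- one-sided 0.05: 45/0.9 = 50, or 45/0.8 = 56.25, rounded up to 57;
- 95% CI rule: 53/0.9 = 58.9, rounded up to 59, or 53/0.8 = 66.25, rounded up to 67, which is above the planned 60.

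**Where the two readings give different answers.** With the SAP's SD and n = 45, the largest observed difference that passes is:

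- one-sided 0.05: 0.03 − 1.680 × 0.00790 = 0.0167 mm;
- two-sided 95% CI: 0.03 − 2.015 × 0.00790 = 0.0141 mm.

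An observed difference between 0.0141 and 0.0167 mm would pass on one reading and fail on the other.

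**Sensitivity of the 93.7% to 98.3% range.**

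- SD recalculated from the SAP's per-eye SD and correlation, 0.095 × √(2 × (1 − 0.85)) = 0.0520: 94.5% to 98.6%.
- Normal approximation with SD 0.053: 94.7% to 98.6%.
- Slightly fewer model degrees of freedom (n − 2 to n − 5): 93.6% to 98.3%.

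**The case against.** The strongest reply is that the contradiction depends on an inference. SAP 4.4 never says two-sided. Section 4.1 attaches that word to means and percentages, not to the difference. The hypothesis is one-sided, only the upper limit decides, and Section 2 sizes the trial "using a one-sided t-test when the margin of non-inferiority is 0.03 mm". Reading Section 4.4 as a one-sided 95% upper bound would make these sections agree. This stands as a possible reading, but it is the less usual one and nothing in the visible text states it. If it was meant, the plan's only success rule still leaves the interval unspecified, so the text needs a change either way.

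A second reply is that comparing a single 98% with a range overstates the gap. That is fair: the stated test has its own range, 96.9% to 99.3%, and does not reach 98% at 40 evaluable either. The like-for-like loss is 1.0 to 3.2 points.

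Third, the trial's size is not threatened. Protocol 9.2 and the table in SAP Section 2 give 80% power, which needs 27 evaluable children under the stricter rule, and at least 40 are expected. This is correct and limits the weight of the point.

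Last, one-decimal powers are finer than the inputs support: SD 0.0520 shifts the range slightly, and the mixed model's covariates are not in the calculation, nor in the SAP's. That is a reason to quote about 94% to 98% as the headline. It does not remove the mismatch.

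**Conclusion.** The point holds and should be fixed. On the natural reading of SAP 4.4, the alpha and the 98% power in SAP Section 2 describe a different test from the one that decides the trial. Power under the written rule is 93.7% to 98.3% over 40 to 54 evaluable children.

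This rests on the SAP's SD of 0.053 mm, a true difference of zero, the paired t-test used for sizing, and the inferred two-sided reading of the 95% CI. The arithmetic is firm; the sidedness is the plan's to state.

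The error is conservative. The stricter rule does not inflate the chance of falsely declaring non-inferiority, and the study remains well powered. The fault is a misstated operating characteristic and an ambiguous primary interval, not an undersized trial.

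**What to change.** Keep the 95% CI rule and write in SAP 4.4 that the interval is two-sided. In SAP Section 2 state one-sided alpha 0.025 and restate the power as about 94% to 98%: 93.7% at 40 evaluable children, 96.0% at 45, 97.0% at 48 and 98.3% at 54.

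If one-sided 0.05 is what the sponsor intends, SAP 4.4 should instead specify a two-sided 90% CI or, equivalently, a one-sided 95% upper bound, and Section 2 should give 96.9% to 99.3% over the same range.

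Either way, align the power statement in Protocol 9.2. The 80% in the SAP Section 2 table is a separate inconsistency with the 98% in the text below it, but it should be reconciled in the same edit so that it does not sit beside the restated figures.

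The cost is a wording change in SAP Sections 2 and 4.4 and one line in Protocol 9.2. If the 95% CI rule is kept, the power for a given number of evaluable children falls by 1.0 to 3.2 points. No additional subjects are needed. The choice should be fixed before database lock.

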4.5 SAFETY ANALYSES

Adverse events will be tabulated by incidence overall, by device related, maximum severity, and those resulting in study discontinuation. Serious adverse events will be listed. Data summarized as well as additional collected data will be provided in supporting line listings. Ocular assessments such as BCVA, biomicroscopic slit lamp, ophthalmoscopy results and other findings will be summarized descriptively.

4.6 MISSING DATA

All possible efforts will be made to minimize missing data rate as missing data may potentially bias the outcome of the statistical analyses and the subsequent estimation of the magnitude of the treatment effect. Due to having only one follow-up visit, it would not be appropriate to impute missing data. Therefore, the efficacy analysis will be completed on the PP population.

4.7 PLANNED INTERIM ANALYSES

There will be no interim analyses during this study.
